1.6. Randomization and Masking

This study is a randomized, double-masked parallel group design. Each subject will be randomized to wear one of two study lenses during the study following the computer-generated randomization scheme prepared by the JJV biostatistician. The randomization will be stratified by study site and randomly permuted in blocks of 2 to achieve a 1:1 ratio of test and control assignments within each study site. The randomization assignment will be completed at the first visit prior to the first lens fitting.

The following procedures must have completed prior to randomize the subjects:

- Obtained Informed consent,
- Confirmed that the subject meets all the inclusion/exclusion criteria, and
- Collected the subject's history and baseline information.

This is a double masked study where the identity of the study lenses will be masked to both subjects and investigators involved in the data collection. The identity of the study lenses will be masked by over labeling the blister packs with a label containing the study number, lot number, sphere power, expiration date, and the randomization codes of T or D. Only the personnel involved in the over labeling and the statistician generating the randomization scheme will have access to the lens decode information translating the randomization codes into the test and control groups. The medical monitor will also have access to the lens decode information in case breaking the mask is necessary for the urgent medical treatment of a subject.

There is an inherent potential risk for unmasking. However, masking will be maintained as much as is logistically feasible. Under normal circumstances, the mask should not be broken until all subjects have completed the study and the database is finalized. Otherwise, the mask should be broken only if specific emergency treatment/course of action would be dictated by knowing the treatment status of the subject. In such cases, the investigator may, in an emergency, contact the medical monitor. In the event the mask is broken, the sponsor must be informed as soon as possible. The date, time, and reason for the unmasking must be documented in the subject record.

Subjects who have had their treatment assignment unmasked are expected to return for all remaining scheduled evaluations. A replacement subject may be enrolled if a subject discontinues from the study prematurely. The decision to enroll replacement subjects will be made by the joint agreement of the Investigator and Sponsor.

2. GENERAL ANALYSIS DEFINITIONS

2.1. Visit Windows

This is a 5-visit dispensing study. Each of subsequent visits should be scheduled approximately a week (6-9 days) following the proceeding visit as shown below.

Table 4: Time and Event Schedule

Scheduled Visit	Time Event	Time Interval (Day)	Target Time Point (Day)
Visit 1	Baseline/Dispensing	0	0
Visit 2	1-Week Follow-up	6 to 9 from Visit 1	7 days from Visit 1
Visit 3	2-Week Follow-up	6 to 9 from Visit 2	7 days from Visit 2
Visit 4	3-Week Follow-up	6 to 9 from Visit 3	7 days from Visit 3
Visit 5	4-Week Follow-up	6 to 9 from Visit 4	7 days from Visit 4

2.2. Pooling Algorithm for Analysis Centers

Data will be pooled from multiple study sites for this analysis. The justification for pooling comes from three critical factors: the study sites follow one common protocol, the sponsor provides close monitoring of study site compliance, and the study sites use common data collection procedures.

2.3. Data Sets

2.3.1. Efficacy Analysis Set

Efficacy analysis set (a.k.a., Per-Protocol data set) includes all subjects who have successfully completed all required visits without any major protocol deviations that the cohort review committee documents as impacting the assessment of the hypotheses prior to the data hard-lock. Justification of excluding completed subjects due to major protocol deviations will be documented in a *Memo to File* and submitted to the trial master file by clinical operation manager.

The following efficacy secondary endpoints will be analyzed on the efficacy analysis set:

- Monocular distance visual acuity 20/20 or better,
- CLUE Comfort Score, and
- CLUE Handling Score.

2.3.2. Safety Analysis Set

Safety analysis set includes all subjects who are administered the test articles and have at least one observation after lens insertion. All safety endpoints will be summarized on the safety analysis set.

The following safety primary endpoints will be analyzed on the safety analysis set:

- Monocular distance visual acuity 20/40 or better,
- Lens fitting acceptability,
- Absolute rotation,
- Stability with blink, and
- Contact lens related corneal staining.

2.4. Definition of Subgroups

No subgroup analyses are planned in this study.

3. INTERIM ANALYSIS AND DATA MONITORING

3.1. Interim Analysis

There will be no interim analysis.

3.2. Data Monitoring

The study will be monitored in a manner consistent with International Conference on Harmonisation (ICH) Good Clinical Practice (GCP). The study monitors will maintain close contact with the Principal Investigator (PI) and the Investigator's designated staff.

Adverse events, protocol deviations, and product quality complaints will be monitored throughout the study. For the purposes of this study the following definitions will apply:

- **Adverse Event:** An AE is any untoward (unwanted) medical occurrence in a patient or clinical investigation subject administered a test article whether or not caused by the test article or treatment. An AE can therefore be any unfavorable or unintended sign (including an abnormal finding), symptom, or disease temporally associated with the use of the test article whether or not related to the test article.
- **Protocol Deviation:** An unanticipated instance when the clinical protocol, as approved by Institutional Review Board (IRB), is not followed.
- **Product Quality Complaint (PQC):** Any written, electronic, or oral communication that alleges deficiencies related to the identity, quality, durability, reliability, safety, effectiveness, or performance of a product after it is released for clinical trial use. PQC is associated with any investigational product (i.e., product manufactured or supplied specifically for a clinical trial).

4. SUBJECT INFORMATION

4.1. Demographics and Baseline Characteristics

Healthy males and females aged between 18 and 40 years will be enrolled in this study. Enrolled subjects must be habitual soft toric contact lens wearers in both eyes. Approximately 50% of study subjects will be habitual monthly replacement modality toric wearers including Air Optix for Astigmatism and Biofinity Toric.

Demographic characteristics including gender, race, ethnicity and age will be summarized by study lens and overall for all enrolled subjects. Continuous variables will be summarized using descriptive statistics (n, mean, standard deviation [SD], median, minimum and maximum) whereas categorical variables will be summarized using frequency table (number and percentage of each category).

4.2. Disposition Information

Accountability (disposition) of all enrolled subjects will be presented by study lens and overall in each of the following subgroups.

- **Completed:** Randomized subjects who are eligible to participate in the study and have successfully completed all required visits.
- **Discontinued:** Randomized subjects who are prematurely discontinued from the study due to any reasons described in the *Protocol Section 5.1*.

- **Total Dispensed:** Subjects who administered the test article at least once (i.e., lens insertion occurred in at least one eye).
- **Enrolled Not Dispensed:** Subjects who are (i) enrolled in the study (provided informed consent) but failed to satisfy the eligibility criteria (inclusion/exclusion criteria), (ii) randomized but discontinued or drop out prior to administering the test article, or (iii) not randomized to treatment for any reason.
- **Total enrolled:** Subjects who signed the informed consent form (i.e., completed + discontinued + enrolled not dispensed).

Efficacy and Safety data sets are defined in Section 2.3.

4.3. Treatment Compliance

Subjects are advised to wear the study lenses for 8 hours each day as daily wear for approximately thirty days. Subject compliance with wearing the study lenses will be recorded at each follow-up visit via electronic data capture (EDC).

Subject's wear time, comfort wear time and percentage of comfort wear time will be descriptively summarized.

4.4. Protocol Deviations

All protocol deviations will be reviewed during the cohort meeting upon study soft-lock. During the cohort meeting, every protocol deviation will be reviewed and classified as either minor or major deviation by cohort committee. Those subjects who deemed to make a major protocol will be excluded from the efficacy analysis set.

All reported protocol deviations will be listed.

4.5. Prior and Concomitant Medications

All reported prior or/and concurrent medications will be listed.

4.6. Discontinuation

All reasons for discontinuation will be summarized.

5. PRIMARY ANALYSIS

All primary analyses will be conducted on the safety analysis set.

5.1. Analysis Specifications

5.1.1. Level of Significance

All planned primary analyses for this study will be conducted with an overall type I error rate of 5%.

The primary analyses (multiple endpoints) will be performed using the intersection-union principal; all primary hypotheses will be simultaneously evaluated using $\alpha = 0.05$. All primary hypotheses must be met in order to claim the success of the study objectives.

5.1.2. Data Handling Rules

Missing or spurious values will not be imputed. The count of non-missing values will be included in the summary tables.

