3.		Left lens insertion	
The investigator or subject will insert the left lens. If the lens is uncomfortable, inspect for damage and remove, reinsert or replace as necessary. If lens damage is present, complete the Product Quality Complaint Form and return the lens to the Sponsor. The lens will be stored in labeled vial with unpreserved saline, and clearly differentiated from the other worn lenses that will be shipped back to the Sponsor
	
4.		Timed settling for left lens	
The investigator will note the time on the stopwatch or timer as soon as the left lens is inserted.
 
At one (1) minute after insertion: Record the rotational position to the nearest degree.
 
At three (3) minutes after insertion: Record the rotational position to the nearest degree.
	
5.		Lens settling	Allow a minimum of 10 minutes of lens settling time.	

6.	Toric Fit Evaluation	
After lens settling, record:
 
 • The rotational position to the nearest degree • Lens stability with blink • Lens stability with eye versions • Toric fit acceptable or unacceptable 
Toric lens fit will be unacceptable if lenses rotated more than 20 degrees, or lens stability is worse than 5 degrees movement with blink. If toric fit is unacceptable, proceed to final evaluation.
	
7.	Subjective spherical over refraction	
Perform subjective spherical refraction over the study contact lens and record the result in visual acuity for OD, OS. Plano or +0.25D must be achieved to continue.
	
8.	Lens modification (if needed)	
Select the reason(s) for lens change (select all that apply):
 
 • The settled lens rotation is such that one of the other available lens cylinder axis would be better (use LARS rule to determine the replacement lens cylinder axis) • The over-refraction is not plano or +0.25 in both eyes • Other (specify reason) 
If one or both lenses are modified, repeat steps 1 through 7 for one or both eyes as appropriate.
 
* If plano over-refraction cannot be achieved, the final sphere should be the most plus/least minus possible for best vision. A maximum of two lens modifications is allowed.
 
If these conditions are not met, proceed to final evaluation.
	
9.	ETDRS Visual performance	
Under high illumination and high chart luminance, record the distance high contrast visual acuity for OD, OS, OU using ETDRS charts at 4 meters.
	

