10.	CLUE Post-Fit Questionnaire	
Subject will complete the CLUE Questionnaire regarding vision and comfort.
	
11.	GSI Questionnaire	
Subject will complete GSI questions regarding their experiences with the study lenses.
	
12.	Subject-Reported Ocular Symptoms	
Record Subject Reported Ocular Symptoms or Problems
	

13.	Lens Fit Assessment	
The general lens fit characteristics will be recorded for both study lenses. These include lens position (centration, limbal exposure, edge lift), and movement (primary and up gaze as well as push-up).
 
Fit acceptability is defined as:
 
 • No limbal exposure (presence of clear cornea) in primary gaze or with extreme eye movements. • No edge Lift • No insufficient/excessive, unacceptable movement in all three movement assessments (Primary Gaze, Upgaze and Josephson Push-up). If lens movement is insufficient and unacceptable in primary gaze and upgaze but is acceptable with the Josephson Push-up technique, the fit will be deemed acceptable. 
*Note: If the lens fit is deemed unacceptable, discontinue the subject and proceed to final evaluation.
	
14.	Lens Deposits	
Front and Back Surface Lens Deposits Back Trapped Debris and Mucin Plugs Lens damage
	
15.	Lens Wettability	Subjective Lens Surface Wettability	

The study lenses being worn will be dispensed.

Step	Descriptor	Details	or Appendix
1.	Distance visual acuity	Record the distance Snellen visual acuity for OD, OS, OU. Subject must keep reading smaller lines until less than half of the letters are correctly identified. Subject must be 20/30 or better OD and OS to continue.	
2.	Dispensing eligibility	Lenses may be dispensed if these conditions are satisfied: 
 • The quality of vision is acceptable to the subject • The lens fit was found to be acceptable. 	
3.	Patient Instruction Guide	Confirm that the subject has received a Patient Instruction Guide. Eye-Cept® rewetting drops may be used as needed by the subjects if lenses become dry during use.	
4.	Lens Care Regimen	Revitalens Ocutec® will be the multipurpose solution for the study. The multipurpose solution is used to rub, rinse and store the lenses when they are not being worn.	

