5.2.1. Definition

Monocular Visual Acuity (VA) 20/40 or better

Monocular VA with the study lenses will be assessed using a Snellen distance VA chart at an optical distance of 20 feet throughout the study. Observed monocular VA collected during the planned visits (Visits 1 through 5) will be dichotomized whether VA was '20/40 or better' (refer as 'acceptable VA') or 'worse'. VA of 20/40 with a negative modifier will consider to be worse than 20/40. Each eye/subject will be categorized into two groups such that 'response=1' if an eye had acceptable VA or 'response=0' otherwise.

Lens Fit Acceptance

Lens fit characteristics will be assessed via slit lamp in terms of lens position, movement and tightness. Each lens fit collected at fitting (Visit 1) will be judged as being either 'acceptable' or 'unacceptable' based on the static and dynamic fit characteristic.

Lens Stability with Blink

Rotational stability with blink will be assessed via slit lamp with beam that can be rotated. The stability of the scribe mark rotational position during a series of normal (unforced) blinks will be observed. Observed rotational stability with blink will be dichotomized whether stability was ' \leq 5-degree' or 'worse' at fitting (Visit 1).

Absolute Rotation

Lens rotation will be assessed via slit lamp with beam that can be rotated. The rotational error (assume shortest distance) and direction (base towards the nose or based towards temple) will be calculated. Absolute rotation will be dichotomized such that 'response=1' if absolute rotation was less than equal to 10-degree (refer as 'acceptable rotation') or 'response=0' otherwise upon 15-minute post insertion at fitting (Visit 1).

Contact Lens Related Corneal Staining (CS)

Contact lens related corneal staining will be assessed via slit lamp throughout the study. Corneal staining will be graded using a 5-level scale; 0=no staining, 1=trace, 2=mild, 3=moderate and 4=severe. Observed corneal staining collected during planned and unscheduled visits will be dichotomized whether the corneal staining is 'grade 2 or lower' or 'Grade 3 or higher'.

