5.2.2. Analysis Methods

Monocular Visual Acuity (VA) 20/40 or better Analysis

Each eye/subject will be categorized into two groups such that 'response=1' if VA was 20/40 or better (refer as 'acceptable VA') throughout all planned visits or 'response=0' otherwise. The generalized linear mixed model (Liang and Zeger, 1986²), as implemented in the SAS/STAT procedure GLIMMIX⁷, will be

used to assess the overall acceptable VA for each lens type utilizing binomial distribution with logit link function. The model will include lens type as a fixed effect and site, subject and eye nested within subject as random effects. Baseline characteristics such as age and gender may be also included in the model as covariates if appropriate.

The model based proportion of eyes with acceptable VA with its corresponding 95% confidence interval (CI) will be constructed for each lens type from the generalized linear mixed model. Overall acceptable VA will be concluded if the lower limit of the 95% CI is greater than or equal to 0.80 (80%).

Lens Fit Acceptance Analysis

Lens fit acceptance at fitting (Visit 1) will be evaluated by lens type if at least 80% of eyes have acceptable lens fit (response=1) using the generalized linear mixed model (Liang and Zeger, 1986²), as implemented in the SAS/STAT procedure GLIMMIX⁷, with binomial distribution and logit link function. The model will include lens type as a fixed effect and site, subject and eye nested within subject as random effects. Baseline characteristics such as age and gender may be also included in the model as covariates if appropriate.

The model based proportion of eyes with acceptable lens fit with its corresponding 95% CI will be constructed for each lens type from the generalized linear mixed model. Acceptable lens fit will be concluded if the lower limit of the 95% CI is greater than or equal to 0.80 (80%).

Lens Stability with Blink Analysis

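### Subjects who leave Visit 1 at the toric-fit or over-refraction step have no lens-fit or study-lens acuity value, and the SAP does not say how VA 20/40 is scored when the visit series is cut short

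*SAP*

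**What the plan says.** **Order of Visit 1 (Protocol 4.7.1).**
- Step 6, toric fit: "If toric fit is unacceptable, proceed to final evaluation".
- Step 7, over-refraction: "Plano or +0.25D must be achieved to continue". Step 8 allows up to two lens modifications, then sends subjects who do not meet the conditions to final evaluation.
- Step 13: general lens fit. It is recorded first, and an unacceptable fit then leads to discontinuation.
- First dispensing step: Snellen acuity with the study lenses, with the rule "Subject must be 20/30 or better OD and OS to continue". The same rule follows the second Snellen reading at Visits 2 to 4.

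**Analysis set and missing data.** All five co-primaries use the safety set (SAP 2.3.2): "Safety analysis set includes all subjects who are administered the test articles and have at least one observation after lens insertion". On missing data, SAP 5.1.2 states: "Missing or spurious values will not be imputed".

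**Endpoints.** For lens fit (SAP 5.2.1): "Each lens fit collected at fitting (Visit 1) will be judged as being either 'acceptable' or 'unacceptable". For VA 20/40 (SAP 5.2.1): "Observed monocular VA collected during the planned visits (Visits 1 through 5) will be dichotomized". SAP 5.2.2 scores an eye 1 if acuity was 20/40 or better "throughout all planned visits or 'response=0' otherwise". Each proportion passes if its lower 95% limit is at least 0.80.

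**The concern.** A subject who leaves at steps 6 to 8 has worn a study lens and is in the safety set, but has no step 13 fit grade and no study-lens Snellen value at any visit. The acuity taken at step 7 is through an over-refraction, and the final evaluation records acuity with refraction, so neither can stand in. Both eyes are lost together, so the subject and eye random effects have nothing to borrow from. The absence is caused by how the lens performed, which makes it informative. The lens-fit and VA 20/40 proportions are then conditional on having passed earlier lens-performance checks.

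A second gap affects VA only. An eye may have acceptable values up to an exit and none afterwards. The SAP does not say whether such an eye was acceptable at all planned visits. Success requires every co-primary to pass, so an unstated scoring rule in one of them could matter.

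**Working it through.** **1. What each exit leaves behind**

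| Exit | Lens fit | VA 20/40 | Seen by another co-primary? |
|---|---|---|---|
| Visit 1 toric fit (rotation over 20 degrees, or blink movement over 5) | missing | no value | Yes: the eye fails rotation (limit 10) or blink stability (limit 5) |
| Visit 1 over-refraction | missing | no value | No |
| Visit 1 general lens fit | recorded failure | no value | Yes: lens fit itself |
| Acuity worse than 20/40 at a visit | recorded at Visit 1 | recorded failure | Not needed |
| Acuity worse than 20/30 but still 20/40 or better | recorded at Visit 1 | acceptable so far, later visits absent | Scoring not settled |
| Fit exit at Visits 2 to 5 | recorded at Visit 1 | that visit's Snellen value is taken first; later visits, if any, absent | Scoring not settled |

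**2. The plan's own figure**

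Inputs from SAP 1.5: success rate 95%, between-eye correlation 0.8, 90 subjects per arm, stated power above 90%. Simulating 90 subjects with two eyes each (20,000 trials; pass if the lower 95% limit is at least 0.80) gives 99.7% to 99.9% power across three intervals: cluster-robust Wald, cluster-robust logit, and Agresti-Coull with effective sample size 2n/1.8. The total also reproduces: 180 × 1.15 = 207.

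**3. Effect of the exits**

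Take 135 Test subjects. A fraction f exits with both eyes, and the remaining eyes succeed at rate p. The documents do not give f, so it is varied.

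Lower limit = q − 1.96 × √[q(1 − q) × 1.8 / (2n)]

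- Exits dropped: q = p, n = 135(1 − f).
- Exits as failures: q = p(1 − f), n = 135.

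For p = 0.95 and f = 10%:
- Dropped: 0.95 − 1.96 × √(0.0475 × 1.8 / 243) = 0.95 − 0.037 = 0.913.
- As failures: q = 0.855; 0.855 − 1.96 × √(0.123975 × 1.8 / 270) = 0.855 − 0.056 = 0.799.

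| f | Lower limit, dropped | Rate, as failures | Lower limit, as failures | Simulated chance of passing, as failures (whole subjects) |
|---|---|---|---|---|
| 2% | 0.915 | 0.931 | 0.890 | 99.9–100% (3 exits) |
| 5% | 0.914 | 0.903 | 0.855 | 97–99% (7) |
| 8% | 0.914 | 0.874 | 0.821 | 64–82% (11) |
| 10% | 0.913 | 0.855 | 0.799 | 16–38% (14) |
| 15% | 0.912 | 0.808 | 0.744 | 0% (20) |

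The simulated ranges cover the three intervals in step 2. With exits dropped or scored 1, the simulated chance of passing is about 100% in every row.

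**4. Tipping point**

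With 135 subjects the observed rate must reach about 0.865 to pass (Agresti-Coull). Setting 0.95 × (135 − k)/135 = 0.865 gives k ≈ 12, or 9% of the arm.

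**5. Historical rate of 100% among remaining eyes**

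With exits as failures, 16 exits still pass (119/135 = 0.881) and 20 do not (115/135 = 0.852).

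**6. False-pass risk**

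Suppose the true rate with exits as failures is exactly 80%. The chance of passing is 2–4% with no exits. If exits are dropped it is 7–11% at f = 2%, 23–33% at 5% and 80–89% at 10%.

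**The case against.** A reader might infer that both endpoints count early exits as successes and are therefore biased toward passing. The documents do not support that.

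- **Lens fit.** It is a Visit 1 endpoint. Failures at step 13 are recorded before the subject leaves, and exits at steps 6 to 8 are missing, not successes.
- **Toric-fit exits.** The failing eye already counts against the trial through rotation or blink stability, and all five co-primaries must pass.
- **Acuity.** An eye at exactly 20/40 meets the endpoint; 20/30 is only a continuation rule. An eye worse than 20/40 is recorded as a failure in the same step. At Visits 2 to 5 Snellen acuity precedes the fit checks.
- **Scoring.** The residual category in SAP 5.2.2 can be read strictly, so that an incomplete or empty series scores 0. Scoring exits as successes is one reading only, so the direction of bias for VA is not established.
- **Size.** SAP Table 2 gives 100% for VA 20/40, lens fit and blink stability, and 97% for rotation within 10 degrees. Rotation beyond 20 degrees would be some part of the remaining 3% of eyes. Counting every exit as a failure is a worst case.
- **Reporting.** The SAP tabulates non-missing counts and summarises discontinuation reasons.

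All of this stands and narrows the point. It does not close it. Over-refraction exits have no historical rate and reach no co-primary. Non-missing counts show that values are absent but do not analyse the absence. The disposition category points to Protocol 5.1, whose reasons do not name these exits. The sensitivity analysis in Protocol 9.1 applies only above 20% dropout and only to efficacy endpoints. The SAP does not repeat it, and SAP 2.3.2 labels the co-primaries safety endpoints.

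**Conclusion.** The point holds in a limited form. Exits at the Visit 1 toric-fit and over-refraction steps remove subjects from the lens-fit and VA 20/40 denominators for reasons tied to lens performance, and the SAP does not settle how a truncated VA series is scored. At historical rates with few exits the effect is negligible. It could decide the result if exits reach roughly 8–10% of Test subjects with about 95% success among the rest.

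This rests on an assumed exit rate. The only related figure is about 15% total dropout, from all causes. It also rests on the planning correlation of 0.8 and on marginal intervals in place of the planned mixed model.

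**What to change.** 1. **Data collection.** Record the general lens fit and study-lens Snellen acuity on the final lens tried in each eye before a subject proceeds to final evaluation. The exit rules stay as they are.
2. **SAP 5.2.** State how VA 20/40 is scored for an incomplete visit series, and which lens counts after a modification.
3. **Sensitivity analysis.** Add an exits-as-failure analysis of VA 20/40 and lens fit on the safety set, not conditional on the dropout rate. Report exits by step and arm.

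Do not code every exited subject's eyes as VA failures in the primary analysis. That would fail sound fellow eyes and eyes that meet 20/40, and would turn acuity into a composite with fit and over-refraction.

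The cost is a little extra recording at Visit 1, a few SAP sentences, one analysis and one table, and possibly slightly less favourable proportions. The first item cannot be repaired once subjects have left.
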